The objective for this study is to determine if daily exercise using All-Stim 2 stimulation of quadriceps muscles will increase leg strength and improve outcomes (duration of hospitalization, long term mobility, long term disability) for mechanically ventilated MICU patients. We plan to randomize patients accepted into this protocol to administration of either sham exercise (i.e. placement of All-Stim 2 units on the legs for 30 minutes a day without activation of the electrical stimulation program) or active exercise (placement of All-Stim 2 electrodes on both legs and stimulating quadriceps muscles to rhythmically contract for 30 minutes a day). The two groups (sham and active exercise) will be treated for 30 minutes a day for seven days. The effects of exercise on quadriceps strength will be assessed by measuring quadriceps force generation (QuadTw) in response to magnetic stimulation of the femoral nerves. The QuadTw assessment will be made immediately before institution of sham or active exercise and will be repeated one day after the conclusion of the seven day training regimen. Chart review and patient follow-up will be used to determine if this treatment regimen has an impact on clinical outcome measures, i.e. duration of hospitalization, long term mobility, long term disability.

**Study Design:** Describe the study design (e.g., single/double blind, parallel, crossover, etc.). Indicate whether or not the subjects will receive placebo medication at some point in the research procedures. Also, indicate whether or not the subjects will be randomized in this study. You may reference sponsor's protocol pages and attach as an appendix in the E-IRB "Additional Information" section, however, a summary paragraph must be provided in the text box below. (Including the study design table from a sponsor's protocol is helpful to IRB members.)

*Community-Based Participatory Research:* If you are conducting [community-based participatory research \(CBPR\)](#), describe strategies for involvement of community members in the design and implementation of the study, and dissemination of results from the study.

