*Research Repositories:* If the purpose of this submission is to establish a Research Repository (bank, registry) indicate whether the material you plan to collect would or would not be available from a commercial supplier, clinical lab, or established IRB approved research repository. Provide scientific justification for establishment of an additional repository collecting duplicate material. Describe the repository design and operating procedures. For relevant information to include, see the UK Research Biospecimen Bank Guidance [\[PDF\]](#) or the UK Research Registry Guidance [\[PDF\]](#)

The basic study design is to:

- (a) obtain informed consent;
- (b) measure magnetic stimulated quadriceps twitch (QuadTw) strength bilaterally;
- (c) randomize patients to treatment with either:

Sham therapy, consisting of bilateral placement of All-Stim 2 electrodes for 30 minutes a day without activation of the electrical circuitry of the unit, or

Active therapy, using the All-Stim 2 electrodes to actively produce a rhythmic quadriceps contraction for 30 minutes a day.

We plan to have a total of 24 patients in the study, with two patients randomized to active treatment for every one patient given sham treatment. As a result we anticipate the final group studied will include 14-16 active treatment patients and 6-8 sham treatment patients.

- (d) continue these regimens daily for 7 days;
- (e) remeasure magnetic stimulated QuadTw on day 8;
- (f) the research team will visit the patient until discharge and will record duration of mechanical ventilation, duration of ICU stay, and total duration of hospitalization; and,
- (g) patients will be visited by a member of the research team at 28 days after study entry to assess the distance that can be walked in 6 minutes (i.e. the 6 minute walk test) and to assess patient well being using the St. Georges Research Questionnaire (SGRQ, a commonly used and extensively validated instrument to assess patient well being).

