**Quadriceps Twitch:** For this assessment, we will place a quadriceps board (Bailey Manufacturing) under the leg, positioned so that the knee lies immediately over the apex of the apparatus. We will then strap a force transducer (Interface, Model SSM-AJ) over the lower leg, positioned at one-fourth the distance between the lateral malleolus of the ankle and the knee. We will first assess twitch force with the apparatus set at the fourth "peg" position, corresponding to a 90o angle between the thigh and lower leg (we have found this corresponds to the optimal angle for quadriceps force generation in the majority of subjects). We will then adjust magnetic field strength during femoral nerve stimulation to ensure optimization of twitch force (i.e. usually at 85% of the maximum Magstim magnetic field strength). Five consecutive twitches will be performed at this setting. Subsequently, to verify the 90o knee angulation setting represents the optimal preload, twitches will be repeated at knee angle settings above and below 90o (i.e. at "peg" settings of 2 and 6). The average of the three best twitch forces generated at the optimal knee angle with supramaximal field strength will be averaged and this measure will be reported as the quadriceps twitch force. The technique will be repeated using the other leg. These measurements should take approximately 20 minutes.

**All Stim 2:** This device consists of a central controller which is attached to four soft adhesive electrodes. Two adhesive electrodes are placed over the quadriceps on each leg (two electrodes on the right, two electrodes on the left for a total of four electrodes). Once these electrodes are positioned, the controller is turned on and a stimulation regimen is selected. We will use a program in

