which 45 Hz frequency current is used, with an on duration of 1 second and an off duration of 3 seconds; current intensity will be increased until the force generated by the quadriceps is 60% of the force generated by the quadriceps in response to magnetic twitch stimulation during the prior preliminary strength testing. (We have performed preliminary tests in normal individuals indicating that this level of force activation is well tolerated and produces a demonstrable reproducible submaximal quadriceps contraction). Once this current intensity is identified, all subsequent training trials will use this level of current density for training studies. Sham training will be performed with a setting of zero current intensity. Stimulation will be carried out as a single session per day with each session lasting 30 minutes.

**Initial Clinical Parameters:** These parameters will be obtained from the medical record using values collected as closely as possible to the time at which initial QuadTw physiological data measurements are made. Parameters will include age, sex, diagnoses, medications, reason for institution of mechanical ventilation, vital signs at the time of the initial visit, bedside parameters of mechanical ventilation use (including mode of ventilation, duration of ventilation, level of oxygen, breath volume and rate, % triggered breaths), most recent arterial blood gas values, and chest radiograph readings. To provide an assessment of pre-hospital function, family members will be asked four questions: (a) how far could the patient ambulate, (b) how many flights of steps could the patient go up, (c) which activities of daily living (dressing, carrying objects, performing daily grooming tasks), if any, were impaired, and (d) did the patient have difficulty standing from a sitting position or lifting objects over their head.

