The PI has studied various aspects of respiratory muscle function and dysfunction over a 25 year period. During this time, the PI has published approximately 100 peer reviewed papers on original research related to respiratory muscle and other critical care topics, as well as 150 abstract presentations at national meetings.

The PI is currently funded by an NIH grant as PI and also receives support as a co-investigator from another NIH grant held by [name]. The PI's laboratory is equipped with a cart containing all the apparatus required to obtain QuadTw measurements. Specifically, the cart is equipped with two MagStim 200 magnetic stimulators equipped with dual figure of eight coils for nerve stimulation, the quad board used for positioning the leg, and a force transducer with a computer interface. This cart is mobile and can be moved to the ICU rooms when needed to assess leg strength. The cart is equipped with sterile wipes that will be used to disinfect all exposed surfaces before and after entrance and exit from patient rooms. Both the Magstim and All Stim 2 units are FDA approved and are in common usage in the USA and other countries for assessment of neurological function and quadriceps conditioning, respectively.

**Potential Risks:** Describe any potential risks or likely adverse effects of the drugs, biologics, devices or procedures subjects may encounter while in the study. Please describe any physical, psychological, social, legal or other risks and assess their likelihood and seriousness.

Use of magnetic twitch stimulation for femoral nerve stimulation is essentially painless. Use of the All-Stim 2 device produces a mild tingling sensation but is also essentially painless at the settings we will use. Removal of the All-Stim 2 electrodes, which have sticky adhesives on their inner surface, could theoretically cause pain in a very hairy individual (this will be dealt with as described below). Both devices could theoretically produce problems in individuals with pacemakers or implanted defibrillators, so patients with these devices will be excluded from the study. We will ask patients to perform a six minute walk test at 28 days after discharge and use a pedometer to assess distance walked. This test has been previously used to assess patient outcomes after ICU discharge (see references 1, 2) with no reported complications. There is essentially no risk to performance of chart reviews or evaluation using the SGRQ.

[Back to Top](#)

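### The sham set-up is described inconsistently, and no stated step hides the visible and felt effects of active stimulation from patients or families before effort-dependent and self-reported day-28 outcomes

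*Combined protocol and SAP*

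**What the plan says.** The control is described in three places in the Research Description of the combined protocol and SAP.

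- **Objectives:** sham is "placement of All-Stim 2 units on the legs for 30 minutes a day without activation of the electrical stimulation program".
- **Study Design, item (c):** sham is "bilateral placement of All-Stim 2 electrodes for 30 minutes a day without activation of the electrical circuitry of the unit".
- **Research Procedures, All Stim 2:** the general set-up reads "Once these electrodes are positioned, the controller is turned on and a stimulation regimen is selected". After the current settings for active training comes "Sham training will be performed with a setting of zero current intensity".

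The same section says that the active current yields a reproducible, demonstrable submaximal contraction of the quadriceps. It is delivered 1 second on and 3 seconds off for 30 minutes. Potential Risks adds: "Use of the All-Stim 2 device produces a mild tingling sensation". Benefit vs. Risk repeats the point about tingling.

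The Study Design prompt asks whether the trial is single or double blind. The answer describes randomisation and the sham but states no blinding. The 28-day follow-up visit collects the 6-minute walk distance, the SGRQ and whether the patient has returned to work. Leg strength is measured by quadriceps twitch force (QuadTw), evoked by magnetic stimulation of the femoral nerves.

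**The concern.** There are two separate issues.

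First, someone setting up a sham session cannot tell from the text whether to switch the controller on. Study Design (c) suggests not; Research Procedures suggests doing so and selecting a program. A reader of the eventual report could not say what the control patients received.

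Second, a sham is meant to keep expectation equal between arms. If patients or families can recognise the arm, effort on the walk test and answers on the SGRQ and about work may shift with no change in muscle strength. These outcomes bear on the mobility and disability aims listed under Objectives.

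**Working it through.** **1. The sham descriptions side by side**

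| Place | What is inactive | Is the sham unit powered? | Current delivered |
|---|---|---|---|
| Objectives | the stimulation program | not stated; fits on or off | none |
| Study Design (c) | the unit's electrical circuitry | natural reading: off | none |
| Research Procedures, All Stim 2 | current intensity set to zero | on, by inference from the general set-up sentence | none |

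The clear conflict is between the second and third rows. In the third, the sham sentence does not itself say that the unit is on. That comes from the set-up step, "the controller is turned on and a stimulation regimen is selected", which is not assigned to either arm. All three agree on electrodes in place and no current.

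**2. What distinguishes the arms**

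| Cue | Active | Sham, unit off | Sham, unit on at zero |
|---|---|---|---|
| Visible contraction | yes | no | no |
| Tingling | yes | no | no |
| Display, light or sound from the controller | not described | not described | not described |

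The two documented cues separate active from sham equally under either version. Harmonising the sham wording alone would leave both in place.

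**3. Which outcomes are exposed**

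- QuadTw is magnetically evoked, so this route does not reach it through patient effort.
- The 6-minute walk depends on effort.
- The SGRQ and return to work are self-reported.

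**4. Illustration of what an assumed bias would do**

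The plan gives no figure to reproduce. Assumptions:

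- The treatment has no effect, but knowing the arm shifts the day-28 mean difference by b standard deviations in favour of active.
- The arms are compared by a two-sample, equal-variance, two-sided t test at 5%. The SAP names t tests and the 0.05 level but does not specify this between-arm test.
- Group sizes are 16 and 8, at the top of the ranges in Study Design (14-16 active, 6-8 sham), or 12 and 6, an assumed number seen at day 28.

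The noncentrality is b × √(n₁n₂/(n₁+n₂)), with n₁+n₂−2 degrees of freedom.

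- 16 and 8: √(128/24) = 2.309, 22 df
- 12 and 6: √(72/18) = 2.000, 16 df

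| b (SD) | Noncentrality, 16/8 | Rejection rate, 16/8 | Noncentrality, 12/6 | Rejection rate, 12/6 |
|---|---|---|---|---|
| 0.2 | 0.462 | 0.073 | 0.400 | 0.066 |
| 0.3 | 0.693 | 0.102 | 0.600 | 0.087 |
| 0.5 | 1.155 | 0.197 | 1.000 | 0.156 |

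These rates apply to a bias of that size from any source. They do not measure the cost of the sham wording or the gain from the fix.

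**The case against.** The strongest reply is that there is one sham, loosely summarised twice and specified once: electrodes on for 30 minutes, no current. Objectives and Study Design are summaries, and Research Procedures is the operating text. On this view only an editorial repair is needed. Much of that stands. The treatment content is the same throughout, and only Study Design (c) is in real tension with Research Procedures. The text still leaves the powered state of the sham unit open.

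A reader might infer that an unpowered sham is what gives the arm away and that the zero-current version would protect the blind. The documents do not support this. No section describes a display, light or sound, and both versions lack contraction and tingling.

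A reader might also infer that different operators ran different shams. Nothing shows this. The sections on recruitment, consent and follow-up point to a very small team, and who runs the sessions is not stated.

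Sedation also limits the problem. The Background says many of these patients need significant sedation and are too obtunded for active exercise, so some will perceive little. That does not limit what a family member at the bedside can see.

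Finally, the consent form is not in the review copy, so what patients and families are told about sham cannot be checked. Suitable neutral wording may already be there.

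**Conclusion.** The point holds in two limited parts. The sham is described inconsistently, with Study Design (c) against the Research Procedures text, and the passages must be reconciled. By itself this changes little, because every version delivers no current. Separately, the plan states no step to conceal contraction or tingling from patients or families, although three day-28 outcomes depend on effort or self-report. The QuadTw comparison is not exposed through patient effort.

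The size of any bias is unknown: the documents do not say how often the arm would be recognised or by how much scores would move. The 7% to 20% rates for 16 and 8 patients illustrate an assumed shift of 0.2 to 0.5 SD. The change is worth making as a cheap improvement in masking. It does not correct a demonstrated bias.

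**What to change.** 1. Replace the three descriptions with one sham procedure, worded identically in Objectives, Study Design (c) and Research Procedures. State whether the controller is on and whether a program is selected. The visible set-up should match the active arm, with no current delivered.
2. In both arms, run every session with the thighs under a sheet and the controller out of view of the patient and family.
3. In the report, state which sham set-up was used for the first 15 patients.

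The continuation review records 15 of the planned 24 patients enrolled and recruitment paused, so the text can be settled before the remaining 24 − 15 = 9.

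The cost is a wording change and a sheet. The operator must lift the cover to check electrodes and contraction, which can briefly expose the arm. An awake patient may still feel the difference, so masking would be improved but not complete.

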Unfortunately, there is currently no specific defined treatment to prevent or reverse muscle weakness in mechanically ventilated patients. Some recent work suggests that vigorous physical therapy, involving cycling exercise of ICU patient, may improve outcomes (3). Such treatments are labor intensive, however, and few ICU's currently have the manpower or equipment to provide such treatments. In addition, many MICU patients require significant sedation and are too obtunded to realistically participate in any active exercise training regimen. In the University of Kentucky MICU patients are supposed to receive 3 treatments of passive range of motion by physical therapists a week, but compliance with this regimen is poor and only a small minority of patients receive even this modest level of therapy. This minimal level of physical exercise for bed bound ICU patients is typical for patients across the country, with the result that many patients who walk into hospitals need to leave in wheel chairs. Depending upon their health insurance status, some of these patients receive outpatient rehabilitation, but many receive little or no therapy even after hospital discharge.

Recently, a number of companies have developed electrical stimulation devices that can exercise the quadriceps, the major leg muscle, by stimulating this muscle to rhythmically contract. This newer technology represents an advance over older electrical stimulators which can be extremely painful and produce potentially injurious robot-like muscle contractions. Currently this technique is being used to provide rehabilitation to leg muscles after knee surgery in orthopedic patients. The purpose of the present study is to use one of these newer stimulators, the All-Stim 2, in mechanically ventilated MICU patients to provide a means of safely, nonvolitionally exercising the leg muscles of these patients. We postulate that this form of treatment will increase leg muscle strength in these patients, reduce the duration of hospitalization, improve long term mobility, and reduce indices of long term disability.

**Objectives:** List your research objectives. You may reference grant application/sponsor's relevant protocol pages and attach as an appendix in the E-IRB "Additional Information" section, however, a summary paragraph must be provided in the text box below.

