**Hospital Outcomes:** After recruitment into studies, electronic hospital records will be reviewed twice a week to determine the time from the point of initial study measurements to successful weaning from mechanical ventilation (defined as remaining off all mechanical ventilation for more than 4 days). Alternative outcomes that will be recorded, for patients that are not weaned from mechanical ventilation, include transfer to a chronic facility for long term weaning from mechanical ventilation (i.e. an LTAC) or death. Deaths will be further subclassified as death due to withdrawal of care and death due to progression of disease. We will also record total ICU stay, total days of hospital stay, and incidence of recurrent respiratory failure, defined as a requirement for reintubation either during the initial hospitalization or at any time out to day 28 after entry into the study. We will also record hospital readmission rates.

**Follow-up Visit (28 days).** At follow-up visits we will assess the distance walked in 6 minutes and we will ask patients if they have returned to work (either full time or part time). We will also have patients fill out the St. Georges respiratory questionnaire (SGRQ) on return visits. This questionnaire evaluates patient's perceptions about their respiratory health, including their assessment of the ability to perform simple tasks of daily living. The PI and/or [name] will visit the patient's domicile (or other site of habitation) to obtain these assessments.

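### ICU stay, hospital stay and the 28-day walk have no rule for death, and stay has none for transfer to a long-term facility, so a raw comparison by arm can mislead if deaths or transfers differ.

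*Combined protocol and SAP*

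**What the plan says.** Background sets out the hypothesis: "We postulate that this form of treatment will increase leg muscle strength in these patients, reduce the duration of hospitalization, improve long term mobility". Objectives repeats it as a test, using chart review and follow-up to "determine if this treatment regimen has an impact on clinical outcome measures, i.e. duration of hospitalization, long term mobility, long term disability".

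Study Design (f) has the team follow patients to discharge; it "will record duration of mechanical ventilation, duration of ICU stay, and total duration of hospitalization". It does not separate live discharge, transfer and death. Hospital Outcomes does name death and LTAC transfer, but only as alternatives to weaning: "Alternative outcomes that will be recorded, for patients that are not weaned from mechanical ventilation, include transfer to a chronic facility". Deaths are then subclassified by cause. Stay follows as a plain duration: "We will also record total ICU stay, total days of hospital stay, and incidence of recurrent respiratory failure".

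Study Design (g) places the walk "at 28 days after study entry to assess the distance that can be walked in 6 minutes". Under Follow-up Visit (28 days), the team "will visit the patient's domicile (or other site of habitation) to obtain these assessments", so a patient in an LTAC can be reached. Potential Risks gives another date: "We will ask patients to perform a six minute walk test at 28 days after discharge".

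The Statistical Analysis Plan is two sentences: t tests before and after therapy with Tukey post-hoc tests, at p < 0.05. It does not mention death, transfer, censoring or missing data. Data and Safety Monitoring assigns the analysis to a board member with a statistics background and sets no rule.

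**The concern.** Death ends a hospital stay. An early death therefore looks like a short stay, and a short stay is the benefit the trial hopes to show. Transfer to an LTAC has the same effect if transfer stops the count. A patient who has died cannot walk, so a survivors-only mean compares different kinds of survivors when mortality differs.

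Death is also likely to be informative here. Background reports that the weakest patients had the highest mortality and the longest ICU stays, and muscle strength is what the treatment targets. Exclusion (l) removes patients expected to have care withdrawn within 7 days, which lowers early deaths without removing them.

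At stake is how the clinical outcomes in the stated objective are read. The arm with more deaths or transfers could look better on stay, or on the walk, with no real benefit.

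**Working it through.** **Inputs from the documents.** 24 patients at 2:1 gives 24 × 2/3 = 16 active and 24 × 1/3 = 8 sham, the top of the stated 14-16 and the matching 6-8. There is no stated mortality, transfer rate, stay, SD or power, so the plan has no figure of its own to reproduce. Every rate below is an assumption.

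**Raw stay.** Let m be mortality, S the mean stay of survivors and D that of decedents, with S and D the same in both arms. The error in (active minus sham) mean stay is (m_sham - m_active) × (S - D). The last column is the share of 200,000 simulated 16 v 8 trials (gamma stays, shape 4) in which mean raw stay favours sham.

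| Mortality active / sham | S / D (days) | Error (days) | Favours sham |
|---|---|---|---|
| 25% / 50% | 30 / 12 | 0.25 × 18 = +4.5 | 77% |
| 25% / 50% | 20 / 12 | 0.25 × 8 = +2.0 | 70% |
| 30% / 40% | 30 / 12 | 0.10 × 18 = +1.8 | 62% |
| 30% / 40% | 20 / 12 | 0.10 × 8 = +0.8 | 59% |
| 30% / 40% | 20 / 16 | 0.10 × 4 = +0.4 | 55% |
| 30% / 40% | 20 / 25 | 0.10 × (-5) = -0.5 | 47% |
| 25% / 50% | 20 / 25 | 0.25 × (-5) = -1.25 | 41% |
| 30% / 30% | 30 / 12 | 0 | 51% |

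The sign turns on whether deaths come before or after survivors' discharge.

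**Noise.** For gamma stays of shape 4, the mean square is 1.25 × mean². At 30% v 40% with S = 30 and D = 12:
- Active: mean 24.6, variance 1.25 × (0.7 × 900 + 0.3 × 144) - 24.6² = 236.3.
- Sham: mean 22.8, variance 1.25 × (0.6 × 900 + 0.4 × 144) - 22.8² = 227.2.
- SD of the difference: √(236.3/16 + 227.2/8) = 6.6 days.

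The same steps with S = 20 and D = 16 give √(92.56/16 + 89.44/8) = 4.1 days. At a 10-point gap the error of 0.4 to 1.8 days sits well inside this noise.

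**Significance.** The nominal rate in one direction is 2.5%. Raw stay is significant in favour of the higher-mortality arm in 2.5-3.7% of trials at a 10-point gap with early deaths (pooled t test). In the first row it reaches about 9% with the pooled test and about 15% with Welch's.

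**Chance gaps.** With identical true mortality of 20-40%, exact binomial calculation for 16 v 8 gives an observed gap of at least 10 points in 59-66% of trials, and of at least 25 points in 20-31%. This is not systematic bias, but one trial's raw stay would then mix length of stay with who died. The chance of no death among 24 is at most 0.8²⁴ = 0.5%.

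**LTAC, if transfer ends the count.** A 10-point transfer gap at day 20 instead of a 30-day stay shifts the mean by 0.10 × (30 - 20) = 1.0 day. A 20-point gap at day 14 shifts it by 0.20 × (30 - 14) = 3.2 days.

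**Walk.** If the extra survivors walk d metres less than the others, the lower-mortality arm's mean falls by d × gap / survival. At 25% v 50% this is 50 × 0.25/0.75 = 17 m to 200 × 0.25/0.75 = 67 m. At 30% v 40% it is 50 × 0.10/0.70 = 7 m to 200 × 0.10/0.70 = 29 m.

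**Cross-check with another model.** With lognormal stays, shared frailty and no treatment effect on underlying stay or walk, 20% v 40% mortality gave raw stay of 19.8 v 16.7 days (+3.1) and a survivors-only walk 11 m lower. That implies d = 11 / (0.20/0.80) = 44 m, near the low end of the range above. Equal death and transfer rates gave no difference.

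**The case against.** The strongest reply is that nothing in the documents says raw means will be compared. The SAP plans no between-arm analysis of any clinical outcome, so harm needs a raw comparison, unequal deaths or transfers, and a particular timing of death. That is correct, and the point is conditional for that reason. But the outcomes are stated objectives, so someone will have to compare them, and the plan gives no method that accounts for death.

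A second reply is that death and LTAC transfer are recorded and a board member with statistical training will do the analysis. This also stands in part: most of the data for a fix will exist. Assigning the analysis to someone does not fix a rule in advance, and 15 of the 24 patients are already recruited.

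A third reply is that noise dominates in a trial of this size. At a 10-point mortality gap it does.

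A reader might infer that the stay result will be biased in a known direction. The documents do not support that: they give no mortality or timing, and the sign reverses if deaths come late. Nor do they support saying that LTAC transfer shortens recorded stay, since whether transfer ends the count is undefined. LTAC patients can be visited for the walk, so they are not lost to it by design.

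**Conclusion.** The gap is real. Stay and the walk have no rule for death, and stay has none for LTAC transfer. Over the assumed cases the mean error in raw stay runs from -1.25 to +4.5 days and vanishes at equal mortality. The survivors-only walk shifts by about 17 to 67 m at 25% v 50% mortality if the extra survivors walk 50 to 200 m less. The main risk is a misleading point estimate on secondary clinical conclusions. It would be too strong to infer frequent false significance, which is modest at a 10-point gap, and equally too strong to rule it out, given about 9% (pooled) to 15% (Welch) in the extreme case. All rates are assumptions; only the missing rules and the conflicting walk dates come from the text. The change should be made, though the trial does not stand or fall on it.

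**What to change.** Before any comparison by arm, add to the SAP:

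1. One pre-chosen method for ICU and hospital stay that accounts for death. For example, ICU-free and hospital-free days from study entry to day 28, compared by rank-sum with death ranked worst; or time to live discharge with death as a competing event and a stated end of follow-up.
2. A rule that LTAC transfer is not recovery or live discharge, with a stated default when LTAC dates are missing. Under either method, patients still in an LTAC at the end of follow-up are tied or censored.
3. The walk analysed by ranks, with death lowest and alive but unable to walk next. Treat the SGRQ in a matching way.
4. Deaths and LTAC transfers reported by arm beside these outcomes, with raw durations kept as descriptive. Confirm that deaths after weaning are captured too.
5. Separately, reconcile the walk date in Study Design (g) with that in Potential Risks. If it runs from discharge, a patient never discharged has no walk date.

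The cost is SAP wording, derived variables and LTAC dates asked at the day-28 visit. Those dates may be missing for the 15 patients already recruited, hence the default.

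Free days can tie heavily. With 25% mortality and 30-day survivor stays (assumed, gamma), 0.487 × 0.75 = 37% are alive with no hospital-free days and 25% are dead. With 20-day stays the first figure is 0.191 × 0.75 = 14%. LTAC patients add to that group, so both figures are minimums. The competing-risk option keeps duration of hospitalization as the outcome, but its effect measure is less familiar and 24 patients give a wide interval.
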